## Background

Adolescence is a vulnerable period for the development of psychopathology, with adolescents experiencing increases in symptoms of depression, certain types of anxiety, and self-injurious behavior. For example, in one epidemiological study, the lifetime prevalence of Major Depressive Disorder (MDD) was 1% up to age 11, but rose to 21% up to age 18 (Hankin et al., 1998). In another epidemiological study, rates of MDD and several anxiety disorders rose steadily over the teen years (Merikangas et al., 2010). Many more adolescents experience high levels of internalizing symptoms without meeting diagnostic criteria for a disorder, and these symptoms may develop into more severe mental health problems in adulthood (Kessler, Avenevoli, & Merikangas, 2001; Leadbeater, Thompson, & Gruppuso, 2012), underscoring the importance of prevention. Self-injurious behavior, in the form of nonsuicidal self-injury, is a prevalent phenomenon among adolescents (Muehlenkamp, Claes, Havertape, & Plener, 2012), and though less common, suicide is the second leading cause of death among adolescents (CDC, 2014). Thus, it is imperative to develop preventive interventions that address these mental health problems faced by adolescents. One way to approach these problems from a public health perspective is to target a transdiagnostic risk factor.

Rumination has been identified as a transdiagnostic risk factor involved in the development of several forms of psychopathology including depression, anxiety and self-injurious behavior (for reviews see Aldao, Nolen-Hoeksema, & Schweizer, 2010; Nolen-Hoeksema & Watkins, 2011; Nolen-Hoeksema, Wisco, & Lyubomirsky, 2008). Rumination involves repetitively focusing on one's negative emotions and brooding about their meaning and consequences (Nolen-Hoeksema, 1991). A meta-analysis showed that rumination is associated with depressive symptoms, concurrently and prospectively among adolescents (Rood, Roelofs, Bogels, Nolen-Hoeksema, & Schouten, 2009), and rumination also prospectively predicts depression diagnosis among adolescents (Abela & Hankin, 2011). Studies have also found that rumination concurrently and prospectively predicts anxiety symptoms in adolescents (e.g., McLaughlin & Nolen-Hoeksema, 2011; Muris, Roelofs, Meesters, & Boomsma, 2004). Finally, rumination has emerged as an important risk factor for both nonsuicidal self-injury (e.g., Hilt, Cha, & Nolen-Hoeksema, 2008; Barrocas, Gilleta, Hankin, Prinstein, & Abela, 2015) and suicidal ideation (e.g., Miranda & Nolen-Hoeksema, 2007; Smith, Alloy, & Abramson, 2006). Given the involvement of rumination in the development of internalizing symptoms and self-injurious behavior, it is an important target for preventive interventions.

Mindfulness meditation is an intervention strategy that has shown promise in targeting rumination. It involves focusing attention on the present moment without judgement (Kabat-Zinn, 2003). Rumination typically involves a perseverative focus on past events (Nolen-Hoeksema et al., 2008), and mindfulness may help alleviate rumination through its focus on the present and emphasis on detaching from mental events, rather than becoming caught up in them as one does while ruminating (Ma & Teasdale, 2004). Trait (i.e., habitual) levels of mindfulness are negatively associated with trait levels of uncontrollable rumination (Raes & Williams, 2010), suggesting these strategies may be antithetical. Indeed, mindfulness meditation interventions have resulted in decreases in distress and negative affect, and decreased rumination appears to be a mediator of these effects (Chiesa & Serretti, 2009).

Mindfulness interventions that show decreases in trait rumination typically involve instruction and home practice over the course of several weeks. For example, an 8-week Mindfulness Based Stress Reduction (MBSR; Kabat-Zinn, 1982) course that involves meeting for two hours once per week along with daily home practice resulted in decreased trait rumination in multiple studies with adult participants (e.g., Deyo, Wilson, Ong, & Koopman, 2009; Shapiro, Brown, & Biegel, 2007). Similarly, a month-long mindfulness intervention with distressed college students showed decreases in trait rumination that were not seen in the active control condition (Jain et al., 2007). Although promising, these intensive interventions have not been examined for their effects on rumination with

adolescents. Furthermore, it is unclear how much practice is required to produce reductions in trait rumination.

Recent work by the PI has shown that a brief mindfulness intervention can reduce state (i.e., momentary) rumination. In two laboratory studies, one with college students (Villa & Hilt, 2014) and one with younger adolescents (Hilt & Pollak, 2012), the PI and her colleagues showed that an 8-minute guided mindfulness exercise reduced state rumination relative to active control conditions. These studies highlight the benefit of even brief mindfulness interventions for adolescents, but they do not show whether occasional or regular use of brief mindfulness exercises would impact trait rumination and subsequent psychopathology.

Because state rumination is positively associated with trait rumination (Moberly & Watkins, 2008), we expect that regular use of brief mindfulness exercises will allow adolescents to repeatedly make state adjustments that will reinforce a behavioral cycle leading to reductions in trait rumination and psychopathology.

## Overview

The primary objective of this study is to examine whether the mindfulness mobile application engages adolescents and reduces rumination and subsequent psychopathology. We hypothesized that adolescents in the mindfulness intervention condition would experience a reduction in symptoms of depression, anxiety, and self-injury relative to those in the control group and that this would be accounted for by a reduction in the tendency to ruminate. We test this by using a randomized, controlled design, comparing the intervention group to a control group that uses the same mobile application for EMA but does not receive the mindfulness exercises.

## Aims of the study and significance

1. To determine whether this intervention may be acceptable and engaging to adolescents.

Participants will report on their satisfaction with the app as well as be offered the opportunity to continue using it during a follow up period beyond the initial intervention period. Their use will be tracked electronically during the 12-week, follow-up period as an indicator of engagement. If the app engages adolescents, it has the potential to be utilized with a large public health impact.

2. To examine whether the intervention reduces state and/or trait rumination and whether this reduction accounts for a reduction in symptoms of psychopathology.

Testing this putative mechanism is an important advancement that has yet to be examined. By comparing the intervention to a control condition, the proposed study will offer a more rigorous test of this research question than the previously completed small pilot studies. Additionally, we will use multiple informants of psychopathology symptoms at pre, post, and follow-up time points, strengthening our outcome measurement. We will also use multilevel modeling to test the effects of state changes in the proposed mechanism and outcomes on trait levels. If the app shows efficacy, it can be tested in a larger trial to determine whether it may be indicated as a wide-scale preventive intervention. If the app reduces rumination, a transdiagnostic risk factor, as hypothesized, it has the potential to prevent many deleterious mental health outcomes.

Mobile applications are needed to address the mental health needs of adolescents. The majority of youth who need treatment for mental health disorders such as depression do not receive it, due to barriers including perceived stigma and inclination toward self-reliance (Gulliver, Griffiths, & Christensen, 2010). Furthermore, the cost of mental health care and lack of available quality care, especially for racial and ethnic-minority individuals, make the

need for new and readily available modes of service, such as mobile mental health care interventions, of tantamount importance (Kazdin & Blase, 2011). Although many mindfulness mobile applications have been developed, almost none have been subject to rigorous empirical investigation (Mani, Kavanaugh, Hider, & Stoyanov, 2015). One randomized, controlled study using a self-selected group of adults showed promise, with those using a mindfulness application 10 minutes per day for 10 days showing a modest reduction in depressive symptoms (Howells, Ivitan, & Eiroa-Orosa, 2016). The proposed study has the potential to serve as a proof of concept that could help inform intervention researchers, clinicians, parents, and educators about the effectiveness of mobile mindfulness exercises for adolescents. This study also has the potential to inform the broader field of mobile mental health. Many mobile mental health applications collect ecological momentary assessment (EMA) data and subsequently recommend customized interventions. However, it is unclear whether the effects are due to the specific mental health intervention, the EMA process or both. By comparing the intervention to a control condition that receives EMA only, I will be able to parse these effects while offering a strong test of Aim 1 (efficacy of the intervention).

In sum, the proposed study addresses the important need of transdiagnostic preventive interventions. Risk for developing psychopathology increases during adolescence, and successful preventive measures can reduce the lifetime burden of psychopathology. For example, preventing a first episode of depression is of great import, given the findings that a first episode results in scars that make future episodes more likely (Rohde, Lewinsohn, & Seeley, 1994; Kendler, Thornton, & Gardner, 2000). The proposed study targets rumination, a transdiagnostic risk factor, using a mindfulness intervention that will be delivered in a format that has the potential for a large public health impact. Furthermore, undergraduate students will be involved in all aspects of the research (i.e., recruitment, scheduling, data collection, analysis, interpretation and presentation), thereby enhancing research training opportunities at the PI's undergraduate-only institution.

### **Sample**

We will recruit 150 adolescent girls and boys, ages 12-15. This age range was chosen to capture the developmental period directly preceding increased rates of depression (Hankin et al., 1998), providing an opportune window for prevention. Participants will be recruited through a recruitment letter mailed to students enrolled in grades 7-10 at a large, local, public school district with over 5000 students in our target age range. In order to maximize the potential of targeting the proposed mechanism, we will only enroll adolescents who report at least moderate baseline levels of trait rumination. This will be accomplished through a 2-question phone screen. Once parents verbally consent and the child has verbally assented, we will ask them to respond to two questions from the Children's Response Style Questionnaire (CRSQ; Abela, Brozina, & Haigh, 2002) that assess brooding, a particularly maladaptive aspect of rumination (Treynor, Gozalez, & Nolen-Hoeksema, 2003). The aggregate of these two questions are highly correlated with the full rumination subscale from the CRSQ ( $r = .79$ ,  $p < .01$ ) and have been associated with depressive symptoms and NSSI in previous work by the PI (Hilt et al., 2008). Adolescents who meet the screening criteria (age 12-15, score of 2 or higher on the brooding questions, and physically and cognitively able to use a mobile application) will be invited to participate in the study. Once they provide written consent and assent, they will be randomly assigned to a condition: EMA only or EMA + Mindfulness at a 1:1 ratio (i.e., ~ 75 participants per condition).

### **Procedure**

Participants and a parent or guardian will come to the laboratory to provide written assent and consent, complete baseline questionnaires, and get the mobile application and instructions. The lab visit will last approximately 40 minutes. We will put the application on participants' own mobile devices (Android or iOS platform) if they have them and loan mobile devices (Android phones without calling services) to participants who do not have their own. The active intervention period will last three weeks, during which time participants will be

asked to use the application at least three times per day. Undergraduate research assistants (RAs) masked to condition will monitor daily use via the database where responses are logged. Midway through each week of the active intervention period, RAs will send reminder messages for motivation and encouragement. A small bonus (\$5 per week) will be offered to participants for protocol compliance (i.e., using the app 21 times that week). The weekly emails will let participants know whether they were on track to receive the bonus or encourage them to use the app more regularly. At the end of three weeks (i.e., post), participants will be notified to complete questionnaires online. At this time, participants still have the opportunity to use the mobile application, but they will not be reminded to use it so that we can monitor self-motivated use. All use will be monitored electronically through a database that tracks responses with time stamps. After six weeks, participants will again be notified to complete questionnaires online (follow-up 1). Finally, after an additional six weeks (approximately 3 months after post), participants will be notified to complete questionnaires online (follow-up 2) and return borrowed phones if applicable (via drop-off, pick up or mail). The total time that participants' use is monitored will be 15 weeks (i.e., 3 weeks for the active intervention period and 12 weeks of follow up). See Figure 1 for depiction of timeline.

[figure not shown]

Figure 1. Overview of participant activities and compensation.

### Questionnaires

At each time point (baseline, post, follow-up 1, follow-up 2), internalizing symptoms will be assessed using multiple informants (adolescent and parent). Additionally, adolescents will self-report on their self-injurious thoughts and behaviors, trait rumination, and trait mindfulness. Finally, parent-reported demographics will be obtained at baseline, and adolescent satisfaction with the application will be obtained at post. Questionnaires will take adolescents approximately 30 minutes to complete and less than 10 minutes for parents. Questionnaires will be completed online using Qualtrics (a survey software platform with secure data storage) except for the demographics form which will be completed on paper to avoid storing any identifying data on the server.

*Internalizing symptoms.* Depression will be assessed using the gold-standard, self-report Children's Depression Inventory (CDI; Kovacs, 1992). This 27-item questionnaire assesses behavioral, cognitive, and physical symptoms of depression and has high reliability and validity ( $\alpha=.88$ ). Anxiety will be assessed using the Multidimensional Anxiety Scale for Children (MASC; March, Parker, Sullivan, Stallings, & Connors, 1997), a 39-item reliable and valid index of anxiety in youth ( $\alpha=.88$ ). It yields a total score along with subscales for physical symptoms of anxiety, harm avoidance, social anxiety, and separation anxiety. Parent-reported internalizing symptoms will be assessed using the 5-item, internalizing subscale from the Pediatric Symptom Checklist (PSC; Jellinek & Murphy, 1988), a widely-used 35-item measure of psychopathology in youth with sound psychometric properties. All of these questionnaires have shown change in response to interventions in previous research.

*Self-injury.* Thoughts and behaviors related to suicide and NSSI will be assessed with the self-report form of the Self-injurious Thoughts and Behavior Interview (SITBI; Nock, Homberg, Photos, & Michel, 2007), a highly reliable and valid assessment tool used with adolescents.

*Rumination.* Trait rumination will be assessed with the rumination subscale from the CRSQ (Abela, Brozina, & Haigh, 2002). This 13-item subscale has demonstrated good reliability and validity ( $\alpha=.88$ ).

*Mindfulness.* Trait mindfulness will be assessed with the modified Five Facet Mindfulness Questionnaire (FFMQ; Baer, Smith, Hopkins, Krietemeyer, & Toney, 2006). This 39-item, self-report questionnaire measures five facets of mindfulness including: observing, describing, acting with awareness, non-judging of inner experience, and non-reactivity to inner experience. The factor structure and construct validity have been demonstrated, and it has high internal consistency ( $\alpha=.80$ ).

*Demographics.* Parents will report on child birth date, sex, race, ethnicity, family socioeconomic status (SES; i.e., occupation, income, family size), and living situation. Adolescents will also report on gender, race, and ethnicity.

*Satisfaction.* Adolescents will answer several questions about the mobile application regarding ease of use and acceptability.

### **Mobile Application and EMA**

There are two versions of the mobile application, depending on the condition: EMA or EMA + Mindfulness. Participants will be randomized using a true randomization procedure (i.e., rolling die with even or odd number determining their condition). The first time they use the mobile application (i.e., during the lab visit), participants enter a unique identification number. Thus, all responses will be logged electronically based on the identification number. Participants are also prompted to enter their wake time and bed time. The application uses this information to time the three daily notifications. Adolescents will be told to respond as soon as possible after receiving a notification, but instructed not to use the phone if they were in a situation where it is not permitted. When accessing the application, adolescents will respond to 10 EMA questions assessing the following:

*Time and place.* Participants are asked whether they are thinking about the past, present, future; whether they are alone or with others and where they are located (e.g., school, home, other). These questions were adapted from a large EMA study (Killingsworth & Gilbert, 2010).

*State rumination.* Participants will respond to two questions regarding focus on emotions and focus on problems using a sliding scale from 0 to 100 for each. These questions were adapted from a previous EMA study on rumination (Moberly & Watkins, 2008) and have been used to assess state rumination in other work (e.g., Hilt & Pollak, 2012; Hilt, Sladek, Doane, & Stroud, 2017).

*State mood.* Using sliding scales ranging from 0 to 100, participants indicate how happy, sad, calm, and anxious they currently feel.

*State mindfulness.* Participants rate their degree of focusing on bodily sensation using a 0 to 100 scale.

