**Specific Aim 2.** Testing of the hypothesis that the intervention will reduce symptoms through the mediating effect of reduced rumination will be accomplished by capitalizing on both trait-level questionnaire data and state-level EMA data. Using trait-level data, an indirect effect model will be tested to examine the effect of condition (EMA-only vs. EMA + Mindfulness) on each outcome (depressive symptoms, anxiety symptoms, parent-reported internalizing symptoms, and self-injury) through the indirect effect of rumination (see Figure 2). These analyses will be accomplished using the PROCESS macro (Hayes, 2013) for SPSS (IBM Corp.) which relies on bootstrapping to generate bias corrected confidence intervals. This approach is particularly well-suited for testing mediation models with relatively small sample sizes. It also allows for the addition of covariates and/or moderators if inclusion of them are warranted. For example, if there are sex differences in rumination and/or symptoms, as is likely based on previous research (e.g., Hilt, McLaughlin, & Nolen-Hoeksema, 2010), sex can be covaried or tested as a moderator of effects (**Exploratory Aim**) using methods described by Preacher, Rucker, and Hayes (2007). Dose can also be examined as a covariate, to test whether variability in use of the mobile application affects outcomes. These indirect effects models will be tested at each time period (post, follow-up 1, and follow-up 2). If the hypothesis is supported for

[figure not shown]

Figure 2. Conceptual indirect effect model. Note that moderators (e.g., sex) may also be included.

the post-intervention time period, it will be helpful to see if effects are maintained at 6 and 12 weeks. If the hypothesis is not supported at the post-intervention period, it will be possible to examine delayed effects at the follow-up time points. For example, the intervention could reduce rumination first and have a delayed effect on symptoms.

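### Each arm is decided by a die roll of which no record is described, so a repeated or overridden roll would leave no trace; a pre-generated, time-stamped list would close the gap, and a household rule should go with it

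*Combined protocol and SAP*

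**What the plan says.** The section Mobile Application and EMA gives the only allocation method: "rolling die with even or odd number determining their condition". It adds that the app exists in two versions, one per condition, and that at first use, during the laboratory visit, "participants enter a unique identification number".

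The Sample section sets the size ("We will recruit 150 adolescent girls and boys, ages 12-15"), the ratio ("at a 1:1 ratio (i.e., ~ 75 participants per condition") and the timing: "Once they provide written consent and assent, they will be randomly assigned to a condition". The Procedure section places written consent, the baseline questionnaires and app installation in one visit. The section Adverse Event says that research assistants obtain consent at that visit. The Procedure section also says that the research assistants who monitor daily use are blinded to arm.

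Data Handling and Record Keeping mentions the file that links IDs to names and the locked paper records. It does not mention an allocation record.

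On households, the Sample section says that participants are "recruited through a recruitment letter mailed to students enrolled in grades 7-10". Eligibility rests on age, brooding score and ability to use an app. No rule covers a second child from the same home.

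**The concern.** Every between-arm conclusion rests on the allocation having been left as it fell. With a die at the enrolment visit, the person holding it may have just met the family, and an unwelcome result can be rolled again. The app database would later show which version a participant used, but not what was first rolled. The documents do not say who rolls, whether the roll comes before or after the baseline questionnaires, or how that person is kept apart from the blinded monitors.

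The analysis would not necessarily absorb a shift. The Statistical Analysis Plan leaves covariates optional and states no adjustment for the baseline value of each outcome.

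A second, smaller gap concerns families. Letters go to four school grades and the eligible ages span 12 to 15, so two siblings may both qualify. Individual rolls can put them in different arms. The control child may then come into contact with the exercises, and one parent would complete the parent-reported internalizing scale for a child in each arm.

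**Working it through.** **Plan's own figure.** Expected arm size is 150 × 1/2 = 75, which agrees with the Sample section. The plan gives no sample-size calculation to reproduce.

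**Is the ratio a problem?** The number in one arm is Binomial(150, 0.5).
- P(exactly 75/75) = 6.5%. The central range is 63 to 87, with coverage 95.9%.
- P(65/85 or more uneven) = 12.1%.
- Relative efficiency of a split a/b is 4ab/150². At 65/85 it is 4 × 65 × 85 / 22,500 = 0.982, a loss under 2%.

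Uneven arm sizes therefore cost almost nothing.

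**Is balance on sex a problem?** Assume 75 girls. The SD of the between-arm difference in the share of girls is √(0.25 × 2/75) = 0.082. A gap of 10 points or more then has probability 22%, and 15 points or more about 6%. The plan allows sex to be covaried, so this is secondary.

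**What could unseen re-rolls do?** These inputs are assumptions, apart from the 150. Distress is standard normal, staff can identify the top 10% (15 children), and half of these (7.5) first roll to control.
- Mean distress in the top 10% is φ(1.2816)/0.10 = 0.1755/0.10 = 1.755 SD.
- If k children move from control to intervention, the expected baseline difference is about 1.755k/(75 + k) + 1.755k/(75 − k).

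| Share of the 7.5 re-rolled | Rule | k | Shift |
|---|---|---|---|
| 25% | one re-roll (half succeed) | 0.94 | 0.022 + 0.022 = 0.04 SD |
| 50% | one re-roll | 1.88 | 0.043 + 0.045 = 0.09 SD |
| 25% | until intervention comes up | 1.88 | 0.043 + 0.045 = 0.09 SD |
| 50% | until intervention comes up | 3.75 | 0.084 + 0.092 = 0.18 SD |

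Simulating 20,000 trials per row gives the same values to two decimals. For scale, the baseline difference under untouched randomization has an SD of √(2/75) = 0.16. Chance of that kind averages zero and is covered by the confidence interval; a shift from re-rolling is in one direction and is not.

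**Would the final counts reveal it?** Suppose 10% of all control rolls were repeated once. Then 150 × 0.5 × 0.10 × 0.5 = 3.75 assignments change and P(intervention) becomes 0.525. The count falls outside 63 to 87 with probability 8.0%, against 4.1% for untouched rolls. With 20% repeated it is 21%. Arm totals are not a usable check.

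**Siblings.** Each enrolled pair is split with probability 1/2. The number of pairs is unknown. P(at least one split pair) = 1 − 0.5^m, which is 50% for m = 1, 88% for m = 3 and 97% for m = 5.

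**The case against.** A fair die cannot be predicted, which is more than can be said of a blocked list with a known block size. It gives 1:1 in expectation, and the plan promises only about 75 per arm. A reader might infer that the method fails to deliver the stated ratio; it does not. A reader might also infer that no log exists and that allocation cannot be verified at all. The documents only fail to describe a log, and the version that each participant used is traceable by ID.

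The re-roll illustration is generous to the concern. Nothing indicates that staff would re-roll or would know who is most distressed: questionnaires are completed online, parent and child sit in separate rooms, and no scoring before assignment is described. If staff impressions correlated 0.3 to 0.5 with distress (assumed), the shift would shrink in proportion: 0.3 × 0.044 = 0.01 to 0.5 × 0.088 = 0.04 SD with one re-roll, and 0.3 × 0.088 = 0.03 to 0.5 × 0.176 = 0.09 SD with rolling until success. Outcomes come from adolescents and parents, not from staff, which limits what an installer who knows the arm can influence.

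On siblings, no enrolment of two children from one home is mentioned. Living with an intervention participant does not by itself deliver the exercises, because the versions differ and sit on separate devices.

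All of this stands, and it limits the size of the point. It does not supply a record of the roll, a named roller or a rule against a second roll, and it does not exclude split siblings.

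**Conclusion.** The point holds as one about traceability. The only allocation method described is a die roll with no described record, and an altered result could not be seen from the arm totals. That the roll happens at the laboratory visit is inferred from the Sample, Procedure and Mobile Application and EMA sections, not stated.

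The possible size is 0.04–0.18 SD of baseline distress. It rests on assumed selective re-rolling by staff who recognise the most distressed adolescents, and the upper half of the range requires rolling until the intervention arm appears. It is not evidence that this occurred or is likely.

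The household gap is real in the text. Its size is unknown, and contamination is a possibility rather than an established effect.

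The change is worth making because the remedy is cheap and every between-arm result depends on the allocation.

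**What to change.** Replace the die with a computer-generated list prepared before the first visit by someone not involved in enrolment, in random permuted blocks of varying size. Stratifying by sex is optional, since sex can be covaried.

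Release each arm only after consent and the baseline questionnaires are complete, with a time stamp and keyed to the participant ID. The app could do this if it can be programmed to; the documents show only that an ID is entered at first use. Otherwise a central or sealed list does the same job. State who obtains the assignment and how that person is kept apart from the blinded monitors.

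Add a household rule: enrol one child per household, or allocate by household so that siblings share an arm. With over 5000 students in the target age range for 150 places, the one-child rule should hardly affect recruitment.

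The cost is a small set-up effort and some protocol wording. Under the one-child rule, a second interested sibling cannot join.
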